**Title:** A comparison of haloperidol 5mg IM vs droperidol 2.5mg and ondansetron for the treatment of hyperemesis in cyclic vomiting syndrome

**NCT#:** NCT05065567

**Date:** 5/19/2025

**Introduction or Background:** Over the past 5 years there has been a 609% increase in persistent vomiting (cyclic vomiting syndrome) related hospitalizations. Many of these have been associated with cannabis use. Despite this significant increase in frequency there is scant literature on the most effective treatment of this condition. A variety of acceptable treatments include ondansetron (Zofran), haloperidol (Haldol) and droperidol. A recent study by Ruberto et al found haloperidol superior to ondansetron for treatment of this condition. Droperidol, a similar D2 agent like haloperidol has been widely used as another treatment option for cyclic vomiting. To date, the two agents have not been compared to determine superiority in managing the symptoms related to cyclic vomiting.

**Problem and Purpose Statement-** The purpose of this study is to compare two commonly used agents for the treatment of cyclic vomiting to see if one agent is inferior to the other in time to improvement in symptoms, need for repeat or rescue medications, treatment failures and complications/side effects. To date, no head to head studies have been published with these two agents.

**Research Questions or Hypothesis:** Is droperidol or haloperidol inferior to the other agent in reducing symptoms related to cyclic vomiting.

**Theoretical Framework-Present Knowledge:** In a recent head to head study, Ruberto et al found that Haloperidol was superior to ondansetron (difference 2.3 cm [95% confidence interval 0.6 to 4.0 cm]; P=.01), with similar improvements in both pain and nausea, as well as less use of rescue antiemetics (31% versus 59%; difference -28% [95% confidence interval -61% to 13%]) and shorter time to emergency department (ED) departure (3.1 hours [SD 1.7] versus 5.6 hours [SD 4.5]; difference 2.5 hours [95% confidence interval 0.1 to 5.0 hours]; P=.03). Haldol, a D2 receptor antagonist, is thought to help suppress the nausea centers of the brain and reduce symptoms from cyclic vomiting. Droperidol, also a D2 antagonist is theorized to have a similar effect. Droperidol has been noted to possibly have a faster time of onset than haloperidol and droperidol is routinely used IV while haloperidol is typically a IM injection.

#### **Methodology:**

This is a clinical trial that will enroll approximately 100 subjects from three different research sites. Patients who have been diagnosed with cyclic vomiting syndrome and enrolled in our study will be given standard treatment of 2.5mg droperidol IV, 8mg ondansetron IV or 5mg haloperidol IM per physician's choice. The research specialist will be notified when the drugs are administered and view the patient's chart to determine if the reason for the anti-nausea drug was a diagnosis of cyclic vomiting syndrome. If so, the patient's nurse will be messaged via EPIC to inquire on the patient's pain and nausea scores initially versus two hours after the drug is administered, if at the St. Joseph ED, research specialist will make contact with the patient and ask pain/nausea scores at baseline and 2 hours later themselves.

Inclusion criteria will be adult patients with a clinical diagnosis of cyclic vomiting in the ED

Exclusion criteria would include pregnancy, allergy to any of the study medicines

Primary outcome will be change in pain and nausea at 2 hrs using a visual analog scale of 0-10

Secondary outcome will be:

1. Change in pain [ Time Frame: 1, 2, 24 and 48 hours ]

Changes in abdominal pain score at 1, 2, 24 and 48 hours vs. baseline

2. Change in nausea [ Time Frame: 1, 2, 24 and 48 hours ]

Changes in nausea score at 1, 2, 24 and 48 hours vs. baseline

3. Treatment success [ Time Frame: 2, 24 and 48 hours ]

Treatment success = both abdominal pain and nausea score < 2 at 2, 24 and 48 hours

4. Discharge ready at 2 hours [ Time Frame: 2 hours ]

Deemed discharge-ready at 2 hours in the opinion of the treating physician

5. Rescue anti-emetics in ED [ Time Frame: at discharge from Emergency Department or 12 hours whichever comes first ]

Given rescue anti-emetics prior to discharge

6. Time to discharge from ED [ Time Frame: at discharge from Emergency Department or 12 hours whichever comes first ]

Time interval to discharge-ready from t=0 (min)

Subject preferred Time to Discharge from ED" > 12 hours (binary yes/no)

7. Return to ED [ Time Frame: 7 days ]

Unscheduled return visits to ED within 7 days (count)

8. Prolonged ED Length of stay [ Time Frame: at discharge from Emergency Department or 12 hours whichever comes first ]

Outcome 10 "

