**Research Design:**

Patients presenting with a chief complaint of vomiting and abdominal pain will be screened by the bedside provider for the diagnosis of cyclic vomiting or cannabis induced vomiting syndrome. Per the doctor's choice, 2.5mg droperidol, 5mg haloperidol or 8mg odansteron will be administered. The remaining portion of the patients care is at the discretion of the treating provider including the use of fluids, laboratory diagnostics and radiographic diagnosis and pain medications. The research specialist will be notified when the drugs are administered and view the patient's chart to determine if the reason for the anti-nausea drug was a diagnosis of cyclic vomiting syndrome. If so, the patient's nurse will be messaged via EPIC to inquire on the patient's pain and nausea scores initially versus two hours after the drug is administered, if at the St. Joseph ED, research specialist will make contact with the patient and ask pain/nausea scores at baseline and 2 hours later themselves. Our research specialist will contact patients 1 and 2 days following treatment and enter responses into the project spreadsheet housed on Spectrum Health Lakeland servers. The provider may, at any time choose to add additional anti emetics at their choice but this will be considered as a "rescue" medication for the purposes of this study. All enrolled patients will be added to a study list where the medication given as well as the the secondary outcomes will be recorded on a secure spreadsheet for analysis later.

Continuous variables (such as pain and nausea score, length of stay in the ED will be analyzed using 2 tailed student t-tests. Qualitative variables (number with 2 point improvement in abd pain and nausea score, discharge state at 2 hours, need for rescue anti-emetic, return to ED) will be analyzed using chi-squared analysis.

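### Pain and nausea scores are first sought after the drug is given, so the baseline is post-dose or recalled at the St. Joseph ED, and no pre-dose score is required elsewhere

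*Combined protocol and SAP*

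**What the plan says.** Methodology and Research Design give the same order of events. The treating physician chooses and gives a drug. Then "The research specialist will be notified when the drugs are administered"; chart review follows, to see whether cyclic vomiting was the reason for it. Scores are sought only if it was, by one of two routes:

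- **St. Joseph ED:** the "research specialist will make contact with the patient and ask pain/nausea scores at baseline and 2 hours later themselves".
- **Elsewhere:** the "nurse will be messaged via EPIC to inquire on the patient's pain and nausea scores initially versus two hours after the drug is administered".

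Two steps are placed before the drug. Methodology says "Patients who have been diagnosed with cyclic vomiting syndrome and enrolled in our study will be given standard treatment", which implies enrolment before dosing. Research Design says that patients "will be screened by the bedside provider for the diagnosis of cyclic vomiting or cannabis induced vomiting syndrome". No pain or nausea score is attached to either step.

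The baseline carries a good deal of weight. Methodology states "Primary outcome will be change in pain and nausea at 2 hrs". Secondary outcomes 1 and 2 are also changes from baseline, for example "Changes in nausea score at 1, 2, 24 and 48 hours vs. baseline". Research Design adds a count of patients who improve by 2 points, and Statistical Analyses reports ANOVAs of baseline against 2 hours after administration for the three drugs.

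**The concern.** A change score is only as good as its starting point. If the starting score is taken once the drug has begun to work, part of the effect is missing from the recorded change. If it is recalled, it carries recall error from a patient who was very unwell at the time.

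An equal loss in every arm would understate each drug's improvement without by itself creating a difference between drugs. The comparison is at risk if the loss is unequal, and the plan gives a reason to expect that it might be: Theoretical Framework says droperidol possibly has a faster onset than haloperidol, and describes one as routinely IV and the other as typically IM. A post-dose baseline would tend to cost a faster drug more of its early effect.

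The collection route also differs by site, and the drug is the physician's choice. If the drug mix differs by site, the way baseline was obtained becomes entangled with the drug given. The documents give no counts by site, so this is only a possibility. With no recorded times of dose and scores, a reader could not check any of it.

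**Working it through.** **Order of steps.** No stated figure in the plan bears on this point, so the main check is a reading of the sequence.

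| Step | St. Joseph ED | Nurse-message route |
|---|---|---|
| Bedside screening for the diagnosis | before the drug, no score | before the drug, no score |
| Drug given | time zero | time zero |
| Specialist notified | on administration | on administration |
| Chart review | after notification | after notification |
| First request for scores | after chart review, from the patient | after chart review, from the nurse |
| Possible source of baseline | current (post-dose) or recalled | charted pre-dose, current, or recalled |
| Later score | 2 hours after baseline, as worded | two hours after the drug |

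Reading the notification as simultaneous with dosing does not change the result, because chart review still precedes the request. Nowhere is baseline defined as pre-dose, given a window, or tied to a recorded time.

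**Timing of the second score.** Statistical Analyses and the nurse route both count from administration. Only the St. Joseph wording counts from the baseline question, so the two need to be reconciled.

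**Illustration of size, within one patient.** The documents give no dose-to-question delay, no onset times, no patients per site and no count of pre-dose baselines, so every input here is an assumption. Let the true fall by 120 minutes be 5 points, with exponential onset of half-life h minutes:

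fall(t) = 5 × (1 − 0.5^(t/h)) / (1 − 0.5^(120/h))

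If baseline is the current state asked d minutes after the dose, the recorded change is:

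- second score timed from the dose: fall(120) − fall(d)
- second score timed from the question: fall(120 + d) − fall(d)

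Worked case, h = 60 and d = 30: fall(30) = 5 × (1 − 0.7071) / (1 − 0.25) = 1.95, and fall(150) = 5 × (1 − 0.1768) / 0.75 = 5.49. The recorded change is 5 − 1.95 = 3.05 (dose-timed) or 5.49 − 1.95 = 3.54 (question-timed).

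| Onset | d = 10: dose-timed / question-timed | d = 30: dose-timed / question-timed |
|---|---|---|
| h = 30 | 3.90 / 3.97 | 2.33 / 2.50 |
| h = 60 | 4.27 / 4.45 | 3.05 / 3.54 |
| h = 120 | 4.44 / 4.72 | 3.41 / 4.20 |
| Linear, continuing past 2 hours | 4.58 / 5.00 | 3.75 / 5.00 |

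The true value is 5.00 throughout. Recall error is not modelled. The table shows how much the baseline time can matter to one patient's recorded change; it does not estimate bias between drugs.

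**The case against.** The time of a request is not the time of a measurement. A nurse asked for an initial score can read a pre-dose value from the chart, and the wording naturally contrasts a starting score with a later one. At St. Joseph the gap between dose and question could be a few minutes, and the protocol does call that score baseline. This stands in part. The documents do not show that any particular baseline was post-dose, and on the nurse route the fault is only that no pre-dose score is required. It does not rescue the St. Joseph wording, under which a pre-dose state can only be recalled.

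The illustration is within-patient, whereas the stated harm is between drugs, and support for an onset difference is one hedged sentence about droperidol and haloperidol that says nothing about ondansetron. That is right, and it is why no between-drug size is claimed. Contrasting the same assumed half-lives (30 against 60, or 60 against 120 minutes, equal true falls) gives dose-timed gaps of 0.17 to 0.37 points at a 10-minute delay and 0.36 to 0.71 at 30 minutes. Question-timed gaps are 0.26 to 0.49 and 0.67 to 1.04. These also rest wholly on assumption.

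The reach is limited. Treatment success, discharge readiness, rescue use and return visits do not use baseline, and Statistical Analyses drops the 24- and 48-hour scores. This is correct, but it leaves the primary outcome exposed.

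Finally, enrolment may be over, since Statistical Analyses is written in the past tense. That shifts weight to the retrospective part of the remedy and does not remove the need for one.

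**Conclusion.** The concern holds. As written, the St. Joseph procedure yields a baseline that is post-dose or recalled, and the other route does not require a pre-dose score. The primary 2-hour change and the ANOVA both depend on that score, so this is more than a missing detail. It should be corrected.

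The size and direction of any bias cannot be determined from the documents. The effect is zero if every baseline is a charted or accurately recalled pre-dose score. Under the assumed inputs above, a 30-minute delay turns a true 5-point fall into a recorded 2.33 to 3.41 points with exponential onset and dose-timed scores. The conclusion concerns the written procedure, not what staff actually did, and confidence is medium for that reason.

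**What to change.** Define baseline as the last pain and nausea scores recorded before the dose. Time the 2-hour score from the dose at all three sites, which brings the St. Joseph wording into line with Statistical Analyses. Record the times of the dose and of both scores.

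**Patients already enrolled (possibly all of them).** Take the charted pre-dose score where one exists, and flag every other baseline as post-dose or recalled. Report the counts by drug and site, and repeat the primary comparison in patients with a verified pre-dose baseline. The cost is one chart check per patient, about 100 in all, and one sensitivity analysis. That subset will be smaller and may be selected, for example by how quickly patients were dosed, so it should be read with that in mind.

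**If enrolment continues.** Write down both scores at the bedside screening that already precedes the drug. Notify the specialist when the drug is ordered rather than when it is given, without delaying the dose. Flag any patient who still has no pre-dose score, because neither step guarantees one. The cost is two scores at an existing step, the recorded times, and some notifications to discard for patients who turn out not to have cyclic vomiting. The cost of moving the notification itself is unknown, because the plan does not say how it is made.

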#### **Ethical Considerations:**

Risks (current and potential).: As all three are standard care the risks are limited to the usual risks associated with treating this condition to include standard medicine reactions, somnolence and dystonic reaction (known with D2 antagonists) and possible QT prolongation (known in all 3 medications). Patients will receive standard care for any side effects of medicine as per standard practice of Emergency Medicine.

**Potential benefits** to the group or class from which the subjects are recruited. Potential benefits to society.

Droperidol has not been commonly used in our emergency departments in the past and if this medicine works better than the others then these patients could experience decreased length of stay and improved time to improvement of symptoms. It is our hope that this project could help guide treatment for this group of patients in the future.

The risk/benefit ratio remains the same whether patients are participating in this study or not. Our clinicians would be using these medicines to treat cyclic vomiting. By formally evaluating response we hope to provide better feedback to physicians going forward with regard to the relative utility of these medicines

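### Primary scores are collected by a different route at the St. Joseph ED than elsewhere, and no analysis compares drugs within site, so a site or route effect on the 2-hour change can enter the drug contrast

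*Combined protocol and SAP*

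**What the plan says.** The Methodology section makes a subjective score the primary endpoint: "Primary outcome will be change in pain and nausea at 2 hrs using a visual analog scale of 0-10". The same section and Research Design both give two ways of obtaining it. By default "the patient's nurse will be messaged via EPIC to inquire on the patient's pain and nausea scores initially versus two hours after the drug is" given. The exception is "if at the St. Joseph ED, research specialist will make contact with the patient and ask pain/nausea scores" at baseline and again at 2 hours.

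On who knows the drug, Methodology says: "The research specialist will be notified when the drugs are administered and view the patient's chart to determine if the reason for the anti-nausea drug". The reason looked for is cyclic vomiting syndrome. No masking of patient, nurse or specialist is described anywhere.

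Treatment is "2.5mg droperidol IV, 8mg ondansetron IV or 5mg haloperidol IM per physician's choice", for about 100 subjects at three sites. There is no randomisation and no stratification by site. Research Design plans two-tailed t-tests for the scores, and Statistical Analyses reports ANOVAs across the three drugs. Neither mentions site or collection route. Research Design lists the drug and the secondary outcomes as what goes on the study list, and does not mention site.

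**The concern.** Pain and nausea ratings can depend on who asks, how and when. Here those conditions are set by site. Drug is also free to vary by site, because each physician chooses. Where site is related to both the measurement and the treatment, an unadjusted comparison of drugs mixes the two. At stake is whether a difference in 2-hour change reported as a drug difference is partly a difference between emergency departments or between ways of collecting the score.

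**Working it through.** The plan gives no figure to reproduce: it states no effect size, standard deviation (SD), power or split by drug or site. What follows is algebra from the described design, then an illustration with assumed inputs.

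**1. What cancels.** Suppose one route adds a fixed amount c to every score. The change is (2-hour score + c) − (baseline + c) = 2-hour score − baseline, so c disappears. Only an effect on the change itself matters. It could come from a different actual time of the 2-hour score, different prompting, other care that differs by site, or floor and ceiling effects.

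**2. What remains.** Let e be the effect on the 2-hour change of being at St. Joseph rather than at another site, with the other two sites taken as alike. Let p_A and p_B be the proportions of drug A and drug B patients who come from St. Joseph. Then:

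unadjusted difference A − B = true difference + (p_A − p_B) × e

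The added term is zero if e = 0 or if p_A = p_B.

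**3. Illustration.** Assumed e is 0.5 to 1.5 points. Assumed shares are 70% and 30%.

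- 0.5 × (0.70 − 0.30) = 0.2 points
- 1.5 × (0.70 − 0.30) = 0.6 points

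For scale, with 33 patients per drug (assumed equal split), two-sided 0.05 and 80% power, the detectable difference between two drugs is SD × √(2/33) × (1.96 + 0.84). That is 1.38 points for an SD of 2 and 2.07 for an SD of 3, both SDs assumed.

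**4. False-positive rate.** This was simulated with no true drug difference, 33 per drug, two-sided 0.05 and 4,000 runs per setting. Each pair gives the rates for SD 2 and SD 3.

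| St. Joseph share by drug | e (points) | False difference, extreme drugs | Unadjusted ANOVA | With site/route term |
|---|---|---|---|---|
| 50/50/50% | 0 to 2 | 0 | 4.8 to 5.5% (all settings) | 4.6 to 5.5% (all settings) |
| 70/50/30% | 0.5 | 0.2 | 6.4%, 6.6% | 5.2%, 5.7% |
| 70/50/30% | 1 | 0.4 | 9.7%, 6.9% | 5.0%, 4.8% |
| 70/50/30% | 2 | 0.8 | 22.7%, 13.0% | 4.7%, 4.7% |
| 80/50/20% | 0.5 | 0.3 | 7.4%, 5.9% | 4.4%, 4.8% |
| 80/50/20% | 1 | 0.6 | 16.6%, 9.0% | 5.2%, 5.0% |
| 80/50/20% | 2 | 1.2 | 49.8%, 26.5% | 5.1%, 5.2% |

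**5. Price of adjusting.** With equal numbers per drug and one two-level site/route term, the variance of A − C is multiplied by 1 + (p_A − p_C)² / [2 × Σp(1 − p)], summed over the three drugs.

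- 70/50/30%: 1 + 0.16 / (2 × 0.67) = 1.119, so the standard error rises by about 6%.
- 80/50/20%: 1 + 0.36 / (2 × 0.57) = 1.316, so it rises by about 15%.

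**The case against.** The best case for the plan is that the endpoint is a change from baseline rated by the patient, that open collection is ordinary in a comparison of standard-care drugs, and that no imbalance between sites is shown. With small effects the false-positive rate stays near nominal, at about 6 to 7% in the mildest settings above. Physician's choice is probably the larger threat. All of this stands. It limits the point to a possibility that the plan neither prevents nor checks.

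Some stronger readings are tempting, but the documents do not support them:

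- A reader might infer that the drug mix does differ by site, because "Droperidol has not been commonly used in our emergency departments in the past". That sentence speaks of the departments together and says nothing about differences between them. Only physician's choice permits an imbalance.
- A reader might infer that nurses estimate the scores. The text fits equally well a nurse who asks the patient and passes on the answer.
- A reader might infer that the specialist's chart review sets St. Joseph apart. It precedes both routes. That the specialist or the nurse knows the drug is a likely inference from the workflow, not a statement in the text.
- A reader might infer that bias is absent only when the drug mix is the same at every site. For the route effect, an equal St. Joseph share across drugs is enough.
- A reader might set the illustration against the 2.3 cm difference cited under Theoretical Framework. That figure compares haloperidol with ondansetron in another trial, and this plan does not adopt it as a target.

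Timing also matters. Statistical Analyses is written in the past tense and drops the 24- and 48-hour data for low response, so the 2-hour data may already be in hand. A change to collection could come too late. The analysis and the reporting can still change.

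**Conclusion.** The point holds as a gap in design and analysis: two collection routes fixed by site, no masking described, drug not balanced across sites, and no site term. Its size cannot be determined from the documents. The 0.2 to 0.6 points rests wholly on the assumed route effect and the assumed 40-percentage-point difference in St. Joseph share, and the value is zero if the shares are equal. The documents do not support saying that the drug comparison is biased. They support saying that the analysis as stated could not detect or remove such a bias, and that a cheap adjustment would remove the between-site part. The point is secondary to confounding by physician's choice, which is a separate matter.

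**What to change.** 1. Tabulate drug by site for all analysed patients. This shows directly whether the shares differ.
2. Add site as a three-level factor to the 2-hour analysis of pain and of nausea, so that drugs are compared within site. As written, route follows from site, so the factor also carries the collection route.
3. State in the report that score collection was unmasked and differed by site.
4. For any patients still to be enrolled, use the same scripted question at all sites. The nurse or specialist only transcribes the patient's own 0-10 score.

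The cost is a table, two degrees of freedom out of about 100 subjects, a sentence in the report and, if enrolment continues, a short script. Site must be recoverable for each patient. Precision falls if drug and site are strongly aligned, as in step 5 of the working. The site term leaves two things untouched: expectation bias within a site, and confounding by physician's choice.

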#### **Informed consent**

Patients experiencing cyclical vomiting exacerbations tend to be very symptomatic and are very uncomfortable. The HAVOC trial (Ruberto et al) experienced low enrollment due to patients not being able to participate in consent discussions. The medicines we are proposing to use are all medicines that have been effective for cyclic vomiting, but it is unknown if droperidol, a relatively recent re-addition to clinicians' pharmacologic armamentarium is better or worse than haloperidol. We feel that since clinicians are going to try droperidol for these patients anyway, we would like to formally assess its utility. We do not want to delay these patients' treatment to go over a lengthy consent document for medicines that will frequently be used in any case, and these patients will often not tolerate carrying this discussion out

**Statistical Analyses:** Means and standard deviations were reported for baseline pain and nausea and for pain and nausea after 2 hours of drug administration for the three arms of the study. ANOVAs were conducted to determine whether significant differences existed between baseline and 2 hours after drug administration for the three drugs. Due to low response rate at 24 and 48 hours (6 pts), these time points were not included in the analysis.

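### No rule is stated for 2-hour scores taken after a rescue anti-emetic, and the chi-squared list names a responder that is not a listed outcome

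*Combined protocol and SAP*

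**What the plan says.** Methodology sets the primary outcome: "Primary outcome will be change in pain and nausea at 2 hrs using a visual analog scale of 0-10". Secondary outcome 3 is "Treatment success = both abdominal pain and nausea score < 2 at 2, 24 and 48 hours". Neither definition mentions rescue, and the 2-hour score is timed only from administration of the study drug.

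Research Design then states: "The provider may, at any time choose to add additional anti emetics at their choice". Such additions are labelled rescue. Other care is "at the discretion of the treating provider including the use of fluids, laboratory diagnostics and radiographic diagnosis and pain medications". Rescue is secondary outcome 5, "Given rescue anti-emetics prior to discharge", with a time frame of ED discharge or 12 hours, whichever is first.

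The analysis paragraph of Research Design lists the variables for chi-squared testing. It includes "number with 2 point improvement in abd pain and nausea score", along with discharge state at 2 hours, rescue and return to ED. Treatment success is not in the list.

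The Statistical Analyses paragraph is written in the past tense: "Means and standard deviations were reported for baseline pain and nausea and for pain and nausea after 2 hours of drug administration". It adds ANOVAs and says that 24 and 48 hours were left out because few patients responded. It mentions no responder analysis and no handling of rescue.

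**The concern.** The study's stated purpose includes comparing the need for rescue and treatment failures. If a second anti-emetic is given at, say, 60 minutes and the patient is comfortable at 2 hours, the plan's definitions allow that patient to be recorded as a success, or as a large improvement, under the first drug. This can flatter whichever drug needs more early rescue. It bears on the 2-hour means and ANOVAs that the Statistical Analyses paragraph describes, as well as on treatment success.

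A second, smaller matter is that a listed binary outcome has no named test, while a binary variable that is not a listed outcome has one. Two responder definitions with no stated priority leave room to choose between them once results are known.

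**Working it through.** **Step 1. Is there a rule for post-rescue scores?** Setting the sections side by side:

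- Treatment success (outcome 3) depends on the two scores only.
- The primary 2-hour change depends on baseline and 2-hour scores only.
- Rescue is allowed at any time, so it can fall before the 2-hour score.
- Outcome 5 is a yes/no up to discharge or 12 hours. A yes may mean rescue at 30 minutes or at 6 hours.
- The Statistical Analyses paragraph is silent on rescue.

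No section says whether a post-rescue score is used as observed, set aside or counted as failure. Use under the first drug is the default consequence of grouping by the drug given.

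**Step 2. Possible size for treatment success.** The documents give no timing of rescue, no success rate after rescue and no droperidol rescue rate. The only rates are those cited in Theoretical Framework from an earlier randomised trial: 31% with haloperidol and 59% with ondansetron. The cited difference reproduces as 31 − 59 = −28 points, with 95% confidence interval −61 to 13.

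Let r be the rescue rate, f the share of rescues given before the 2-hour score, and s the success rate after such rescue. Assume the same f and s for both drugs. Score-only success exceeds rescue-free success by r × f × s.

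| f | s | haloperidol | ondansetron | gap (points) |
|---|---|---|---|---|
| 0 | any | 0 | 0 | 0 |
| 0.25 | 0.5 | 3.9 | 7.4 | 3.5 |
| 0.5 | 0.5 | 7.75 | 14.75 | 7.0 |
| 1 | 0.5 | 15.5 | 29.5 | 14.0 |
| 1 | 1 | 31 | 59 | 28.0 |

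Putting the interval limits through f = s = 0.5 gives −61 × 0.25 = −15.25 and 13 × 0.25 = +3.25 points (haloperidol minus ondansetron). Either sign is possible.

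**Step 3. Possible size for the primary change.** Let d be the mean observed improvement, on either score, of patients rescued before 2 hours (assumed 2 to 6 points). Setting their change to zero lowers a drug's mean improvement by r × f × d. The between-drug shift is (0.59 − 0.31) × f × d. At f = 0 it is zero. At f = 0.5:

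- d = 2: 0.28 × 0.5 × 2 = 0.28 points
- d = 4: 0.28 × 0.5 × 4 = 0.56 points
- d = 6: 0.28 × 0.5 × 6 = 0.84 points

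At f = 0.5 and d = 4, the interval limits give −0.26 (−0.13 × 2) to +1.22 (0.61 × 2), taken as ondansetron minus haloperidol.

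Zero change removes everything that a rescued patient gained, including any gain before rescue. If only the points gained from rescue are removed (g, assumed 1 to 3), the shift at f = 0.5 is 0.28 × 0.5 × g = 0.14 to 0.42 points.

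**Step 4. Are the two responders interchangeable?** No. A patient going from 9/9 to 7/7 improves by 2 on both scores but is not a success. A patient going from 3/3 to 1.5/1.5 is a success but improves by only 1.5. The entry rule, "Inclusion criteria will be adult patients with a clinical diagnosis of cyclic vomiting in the ED", sets no minimum score, so neither pattern is excluded. The 2-point item also does not say whether both scores must improve.

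**The case against.** The best defence is that scores as observed are a legitimate choice in a study where the physician picks the drug and directs the remaining care. Rescue is reported as its own outcome with its own test, so it is not hidden. This stands: observed scores should be kept. It leaves a gap, because outcome 5 cannot show whether rescue came before the 2-hour score, and the plan does not say that observed scores are its choice.

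It can also be said that the proposed analyses do not isolate the first drug's effect and bring provider preference into the success definition. This stands too. They show how far the result depends on early rescue, and no more.

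The illustrations are weak evidence, since f, s, d and g are all assumed. The cited rates concern haloperidol and ondansetron, while the stated hypothesis concerns droperidol and haloperidol. The cited trial's title says that haloperidol was intravenous, whereas here it is intramuscular.

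On the responder wording, treatment success is a binary variable and could fall under the chi-squared class without being named. The list is not a full inventory: the item on discharge beyond 12 hours in outcome 6 is also missing. The ethics text describes these patients as very symptomatic, so low-baseline cases such as 3/3 may be uncommon.

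**Conclusion.** The point holds as a cheap improvement. The definitions allow a patient rescued before 2 hours to be counted as a success or improver of the first drug, and nothing in the plan lets a reader see how often that happens. The possible shift runs from none (no rescue before 2 hours) to several points of success or a fraction of a scale point under middling assumptions. These figures are illustrations with common f, s, d and g across drugs, not bounds. Nothing in the documents sizes the droperidol comparison.

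Three stronger readings are tempting and not supported:

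- A reader might infer that the described 2-hour results are biased towards a particular drug. The documents give no rescue timing, and the cited interval allows either direction.
- A reader might infer that treatment success was replaced by the easier 2-point responder. Research Design does not say that one replaces the other, and the Statistical Analyses paragraph reports neither, so no described result rests on the mismatch. It matters only for responder results still to be reported.
- A reader might treat the loss of 24 and 48 hours as an undisclosed change to outcome 3. The Statistical Analyses paragraph states the omission and its reason, so no rewriting of outcome 3 is needed.

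**What to change.** 1. Keep the 2-hour scores as observed, and state that this is the choice.
2. Beside them, report 2-hour treatment success with patients given a rescue anti-emetic before the 2-hour score counted as non-success, using administration times from the chart. Add one sensitivity analysis of the primary 2-hour change for the same patients, for example with change set to zero, noted as a harsh assumption for anyone who had partly improved before rescue.
3. Name 2-hour treatment success in the chi-squared list. Label the 2-point improvement exploratory and say whether both scores must improve.
4. Date these additions and label them post hoc, because the analyses are already described as done. State that drug choice, rescue and pain medication are at the provider's discretion, so neither version isolates the first drug's effect.

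The cost is wording, one re-analysis of scores already collected, and a check of rescue times for rescued patients only. That is 31 to 59 charts if the cited rates applied to all of about 100 patients (0.31 × 100 and 0.59 × 100); the research specialist already views the chart. Success rates can only stay the same or fall in the rescue-free version, and provider preference enters it. Patient care is unchanged; only scoring and reporting change.
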